11.4 Secondary analyses

A strategy similar to that used for the primary endpoint will be employed for secondary endpoints. For other HR-QOL type endpoints (e.g., ability to eat, days of nasogastric tube, intravenous hydration, solid food, etc.) we will examine the distribution properties of these variables and determine whether a normal approximation is adequate, or whether a transformation would be required or another generalized linear model would be preferable. For failure time endpoints, such as overall survival, the analyses will be based on a Cox regression model where we will have the option of stratifying on study component and selected other key covariates rather than modeling them in the regression. QALY-adjusted analyses will incorporate the EQ-5D-5L, as described in Cheville et.al. (44)

Specific to dietary outcomes we will describe total self-reported energy intake, macronutrient intake in patients with MBO and relation to time since MBO and if this differs for those undergoing surgery versus no surgery. Similarly we will evaluate the same associations with the dietary exposure of interest being frequency of meals and alternately composition of meals (liquids, solids, mixed, feeding formulas [oral or enteral]).

Adherence adjusted analyses: Although the primary analysis will be based on the intent to treat (ITT) principle, if a substantial fraction ($> 30\%$) do not receive the initially assigned/chosen treatment, we will conduct a sensitivity analysis that takes into account the patient's received treatment through inverse probability weighting.

In exploratory analyses we will examine the extent to which we can identify subgroups of patients for whom differences in treatment effects may differ from the overall result, i.e.,

are there subgroups of individuals for whom surgery is particularly beneficial or particularly contra-indicated? To address this question, the final model for the primary analyses in the pooled data will be expanded using interaction terms between selected baseline factors and treatment assignment.

Sample sizes permitting, those of particular interest will be analyzed based on the following hypotheses:

1. Patients with ascites who undergo a surgical procedure will have poorer outcomes than those who are treated by non-surgical management.
2. Patients who have albumin < 3.0 who undergo a surgical procedure will have poorer outcomes than those who are treated by non-surgical management.
3. Patients with carcinomatosis evident in more than one quadrant of the abdomen who undergo a surgical procedure will have poorer outcomes than those who are treated by non-surgical management.

Additional analyses will be conducted in the non-randomized component to examine predictors of treatment, and the diversity of treatment within each arm (e.g., type of surgical procedure and medications used), patterns of care over time, including the frequency with which a patient initially selecting one treatment approach is crossed over to the other strategy, etc.

11.5 Sample size

Our goal is to randomize at least 50 eligible patients, in equal proportions, to surgical or non-surgical care and register 130 eligible patients to the non-randomized component. Available data from 144 patients for whom number of good days could be determined show the mean number of good days of 33 with standard deviation of 25. With a total of 180 eligible patients with equal numbers in each treatment group, we would have 90% power to detect a 14-day difference in the mean number of good days using a two-sided, 0.05-level t-test. We have increased the overall target sample size to 200 to allow for potential losses to follow-up and incomplete data, for potential inefficiencies associated with imbalance in the number treated in each group in the non-randomized component and for the need to adjust for differences in baseline characteristics. For an analysis restricted to the trial alone with 50 patients randomized, the power would be .51. While this is a low power for a trial, we know that fear of randomization represents the dominant reason patients give for refusing to participate in clinical trials so to help assure adequate accrual, the sample size of the randomized component is small. (45)

Updated sample size: In October 2017, the DSMC recommended that “after the cohort accrual goal is reached, the randomization portion of the trial may continue for a probationary six-month period. The DSMC would then carefully evaluate the feasibility of randomizing patients to this trial and evaluate the ability achieve the objectives of the trial.” This recommendation followed the observation that accrual to the randomized arms has been considerably slower than expected. Accrual to the two treatment arms in the non-randomized cohort was also found to be unbalanced, favoring the non-surgical arm by more than 2:1. In accordance with the monitoring plan, the sample size targets are hereby adjusted to reflect the DSMC’s recommendations. Accrual to the non-randomized arms will continue until 166 patients have been registered in the non-randomized arms, with specific efforts to increase enrollment in the surgical choice arm. After the non-randomized arms are closed, the study will continue to accrue patients to

the randomized component during the subsequent six months. At that time, the DSMC will evaluate the feasibility of continuing to full accrual is reached (200 patients total). June 2019 update: With the closure of the non-randomized component (with 165 of the targeted 166 patients) and the recent success in accruing patients to the randomized component (with 34 now randomized), the study has demonstrated the feasibility of meeting the original randomization goal. The study investigators have requested and the NCI has approved an increase in total accrual to 220, which would allow the randomized component to reach the initial target of 50 eligible patients randomized, consistent with the design as originally conceived.

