11.3 Primary analyses

All eligible patients will be included in the analysis using the general modeling strategy pioneered by Prentice et al. for pooling data from a randomized trial and parallel non-randomized component. (33,34,35,36,37) For randomized patients, the analysis will be based on their assigned treatment according to the intent to treat (ITT) principle. For the non-randomized component, a pseudo-ITT approach will be used where patients will be included in the treatment group identified at enrollment as their initially chosen care plan (surgical versus non-surgical), as documented at registration. The primary analysis will pool data from both components using a multivariate linear regression model (after possible rescaling, if necessary to improve the distribution assumptions), including a parameter for study component. Factors considered likely to confound the association of treatment and outcome in the non-randomized component will be carefully modeled in the regression. Potential residual bias in the treatment group comparison from the non-randomized component will be assessed by estimating the interaction term between treatment group and study component (randomized vs. non-randomized). If, after adjustment for covariates, there is no evidence of substantial bias, the main treatment effect parameter in the reduced model (without the interaction term) will serve as the

basis for inference. If there is evidence of significant bias in the non-randomized component relative to the randomized component, the estimates from both the randomized and non-randomized components will be reported but the primary analysis will be based on the randomized component alone.

If the approach of Prentice et al., proves unwieldy because the number of covariates required to adjust for imbalance in the non-randomized component is too large for the sample size available, we will pursue the use of propensity scores. (38,39,40,41,42,43) In this approach, a logistic regression model would be developed in non-randomized component data to estimate the probability of selecting surgery using the baseline covariate data, both from patients and providers. The propensity score for each patient is then simply the estimated probability; this score can be used in the regression model instead of adjusting for individual confounders.

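### Section 11.5 states 90% power for a 14-day difference with 180 patients in equal groups; its own inputs give 96%, and 90% power corresponds to about 12.1 days

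*Combined protocol and SAP*

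**What the plan says.** Section 11.5 (Sample size) takes its planning values from 144 earlier patients, whose data "show the mean number of good days of 33 with standard deviation of 25". The power statement supposes 180 eligible patients divided evenly between surgery and non-surgical care, and claims: "we would have 90% power to detect a 14-day difference in the mean number of good days using a two-sided, 0.05-level t-test".

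The next sentence deals with what could erode that power: "We have increased the overall target sample size to 200 to allow for potential losses to follow-up and incomplete data". It names two further reasons for the increase, namely unequal group sizes in the non-randomized component and adjustment for baseline differences.

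For the randomized patients on their own, who are to be allocated equally, the section says: "For an analysis restricted to the trial alone with 50 patients randomized, the power would be .51".

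Section 11.3 (Primary analyses) makes both figures relevant. The pooled model is primary unless there is evidence of significant bias in the non-randomized component; in that case "the primary analysis will be based on the randomized component alone".

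**The concern.** The power sentence contains everything needed to check it: group sizes, difference, test, significance level and sidedness, with the standard deviation just before it. The check gives a figure about 6 percentage points higher than the one printed. In terms of type II error, that is about 3.8% against the 10% implied.

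The direction is conservative, so nobody is led to run too small a trial. What is at stake is interpretation. A reader takes 14 days to be the difference detectable with 90% power in the ideal equal-group case, when the stated inputs put it near 12.1 days. A reader also cannot tell whether 90% is a slip or contains an allowance that is not described. Because Section 11.3 lets the primary result come from either the pooled data or the randomized patients alone, the two powers in Section 11.5 should rest on the same inputs.

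**Working it through.** **Inputs, all from Section 11.5:** standard deviation 25 days; difference 14 days; two-sided 0.05 t-test; 90 per group for the 180-patient statement; 25 per group for the randomized patients alone.

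**1. The stated 90%, from its own inputs**

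- Standard error of the difference = 25 × √(2/90) = 3.727 days.
- Standardized difference = 14 / 3.727 = 3.757.
- Normal approximation: power = Φ(3.757 − 1.960) = Φ(1.797) = 0.964.
- Noncentral t with 178 degrees of freedom: 0.962.

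The 90% is not reproduced.

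**2. What 90% power corresponds to**

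- Detectable difference with 90 per group = 3.727 × (1.960 + 1.282) = 12.08 days (normal), or 12.15 days (noncentral t).
- Patients needed for 14 days = 2 × (25/14)² × (1.960 + 1.282)² = 67.0 per group (normal), or 67.99 (noncentral t). That is 68 per group, 136 in total, and power at 136 is 0.900.

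**3. Cross-check on the .51**

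- Standard error with 25 per group = 25 × √(2/25) = 7.071.
- Power = Φ(14/7.071 − 1.960) = Φ(0.020) = 0.508 (normal), or 0.492 (noncentral t).

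The .51 agrees with 14 days and a standard deviation of 25 under the normal approximation, and is within two points under the t-test.

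**4. Could another assumption give 90%?** (noncentral t, 14 days; standard deviation 25 unless noted)

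| Assumption | Power | Fits the text? |
|---|---|---|
| 10% of the 180 lost (81 per group) | 0.943 | Losses are covered by the step to 200 |
| Overall split 2:1 of 180 | 0.941 | Text says equal groups |
| Overall split 3:1 of 180 (45/135) | 0.899 | Text says equal groups |
| Two-sided 0.025 | 0.932 | Text says 0.05 |
| Two-sided 0.01 | 0.874 | Text says 0.05 |
| Standard deviation 28.8, 90 per group | 0.900 | Text says 25; power with 50 patients would be 0.39, not .51 |

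Reaching 90% through loss alone would mean losing 44 of 180 (24%) or 64 of 200 (32%). No such rate is stated, and going from 200 back to 180 is a 10% loss. If all 200 were evaluable in equal groups, power would be 0.976.

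**The case against.** Four points can be made on the other side.

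- **The consequence is small.** Understated power does no harm to the design: no endpoint, analysis, decision rule or patient is affected. This stands, and it makes the point one of accuracy in reporting, not of trial size.
- **The 180-patient plan has been overtaken.** Section 11.5 later reports non-surgical choice ahead by more than 2:1 in the non-randomized cohort, raises total accrual to 220, and the document is stamped closed in May 2020. This is true. However, the sentence is still current text, and none of the updates restates power, so it remains the only power statement for the pooled analysis.
- **The pooled analysis is not an unadjusted t-test.** Section 11.3 specifies a regression with covariates and a term for study component. Adjusting for factors related to treatment choice can inflate the variance of the treatment effect. As an assumption, since the documents give no figure, inflation by 1.2 would bring power with 180 patients to about 0.93, and inflation by 180/136 = 1.32 would bring it to 0.90. Covariates that predict outcome would work the other way. This stands as a caution about wording: 96% is the power of the simplified test the sentence names, and should be labelled so. It does not rescue the 90%, because the sentence specifies a t-test and the section assigns adjustment to the increase to 200.
- **The .51 is only indirect evidence.** That sentence does not repeat the difference, the standard deviation or the test, and the exact t-test gives 0.492. This is fair: the .51 is consistent with the stated inputs but does not prove they were used. The main result does not depend on it.

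**Conclusion.** The concern holds. On the inputs in Section 11.5 (standard deviation 25, 90 per group, two-sided 0.05 t-test), power for a 14-day difference is 96.2%, or 96.4% by the normal approximation. The stated 90% is too low by about 6 points. The difference detectable with 90% power is about 12.1 days, not 14. Getting to 90% needs an assumption that the text either excludes or does not mention.

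The result assumes that the stated inputs are the intended ones and that all 180 patients are evaluable. It concerns the unadjusted calculation in the original plan, not the power of the adjusted model at the sample finally accrued.

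**What to change.** Restate the sentence in Section 11.5 along these lines: *with 180 eligible patients in equal groups and a standard deviation of 25 days, an unadjusted two-sided 0.05 t-test has 96% power for a difference of 14 days, and 90% power for about 12.1 days.* Say that this refers to the original 180-patient plan.

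If 90% was meant to include a further allowance or a larger standard deviation, state that instead and recompute the randomized-only power with the same inputs. In either case, give the difference, standard deviation and method behind the .51.

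The cost is the wording of one paragraph, with no change to enrolment or analysis. As the study is stamped closed, the correction can go in a clarification to the SAP or in the sample-size statement of the study report.

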11.6 Estimate of Accrual Rate

The anticipated accrual rate is based on the number of potential study patients available at the participating institutions. Conservatively, there will be at least 350 potential patients per year at the participating institutions with the presenting diagnosis of MBO based on the study definition. Due to multiple factors, expected accrual each year will be significantly less than 350 patients. Reasons include ineligibility, patient refusal, or inability to recruit the patient in the prescribed 3 working days post-surgical consultation criteria. SWOG has no prior experience in recruiting these patients to draw from so we have set a target of 6 patients/month, which would allow for complete enrollment in 3 years, including IRB approval and study ramp-up time.

11.7 Trial Monitoring

A Data and Safety Monitoring Committee will oversee the conduct of the study. The Committee consists of four members from outside of SWOG, 3 SWOG members, 3 nonvoting representatives from the National Cancer Institute (NCI), and the Group Statistician (non-voting). The members of this Committee will receive confidential reports every 6 months from the SWOG Statistical Center, and will meet at the Group's bi-annual meetings as necessary.

Trial monitoring will focus on accrual, with particular attention to the rate of accrual to the randomized component as well as the distribution of the selected treatment in the non-randomized component and comparison of baseline characteristics between the randomized control trial and non-randomized components. If after 12 months of active recruitment at the key participating centers, accrual to the randomized component is less than 12, we will consider a redesign to complete accrual as a non-randomized study only. If there is evidence of the ability to recruit a larger number of patients to the randomized comparison, we will consider limiting the non-randomized component enrollment. Similarly, if during the course of the trial we learn that a large fraction of patients are not adhering to their assigned treatment, we will consider discontinuing the randomized control trial portion. For the non-randomized portion, if a large fraction (75%) of patients are not adhering to their initially chosen treatment, we will consider closing accrual to the over-subscribed arm, either temporarily or permanently. These decisions will be made blinded to all information on endpoint comparisons. If after 12 months of active recruitment at the key centers, accrual to the overall study is less than 30, we will consider stopping based on infeasibility of recruitment.

No formal interim analyses for efficacy or safety are planned for several reasons. Both of these treatment options are commonly used in clinical practice. These patients are in very advanced stages of disease and deaths are expected. The randomized component, on its own, is underpowered and, in total, represents the minimum information one might expect to have at an interim analysis of a full-scale trial. If accrual to the randomized portion is substantially greater than anticipated, so that the expected number randomized

exceeds 100, we will institute a single interim analysis when the data are complete for 50 randomized patients.

12.0 DISCIPLINE REVIEW

Discipline review is not necessary for this study.

13.0 REGISTRATION GUIDELINES

13.1 Registration Timing

Patients must be registered to the study within 3 working days after surgical consult for MBO or within 3 days after completion of indicated treatment (e.g. TPN, anticoagulation reversal) to make them eligible for surgical intervention, whichever is later, and prior to any treatment for MBO (no more than two working days prior to planned start of treatment).

13.2 Investigator/Site Registration

Prior to the recruitment of a patient for this study, investigators must be registered members of a Cooperative Group. Each investigator must have an NCI investigator number and must maintain an "active" investigator registration status through the annual submission of a complete investigator registration packet to CTEP.

a. CTEP Registration Procedures

Food and Drug Administration (FDA) regulations and National Cancer Institute (NCI) policy require all individuals contributing to NCI-sponsored clinical trials to register and to renew their registration annually. To register, all individuals must obtain a Cancer Therapy Evaluation Program (CTEP) Identity and Access Management (IAM) account (<https://ctepcore.nci.nih.gov/iam>). In addition, persons with a registration type of Investigator (IVR), Non-Physician Investigator (NPIVR), or Associate Plus (AP) (i.e., clinical site staff requiring write access to OPEN, RAVE, or TRIAD or acting as a primary site contact) must complete their annual registration using CTEP's web-based Registration and Credential Repository (RCR) (<https://ctepcore.nci.nih.gov/rr>). Documentation requirements per registration type are outlined in the table below.

Documentation Required	IVR	NPIVR	AP	A
FDA Form 1572	✓	✓		
Financial Disclosure Form	✓	✓	✓	
NCI Biosketch (education, training, employment, license, and certification)	✓	✓	✓	
HSP/GCP training	✓	✓	✓	
Agent Shipment Form (if applicable)	✓			
CV (optional)	✓	✓	✓	

An active CTEP-IAM user account and appropriate RCR registration is required to access all CTEP and CTSU (Cancer Trials Support Unit) websites and applications. In addition, IVRs and NPIVRs must list all clinical practice sites and IRBs covering their practice sites on the FDA Form 1572 in RCR to allow the following:

- Added to a site roster

- Assigned the treating, credit, consenting, or drug shipment (IVR only) tasks in OPEN
- Act as the site-protocol PI on the IRB approval

Additional information can be found on the CTEP website at <<https://ctep.cancer.gov/investigatorResources/default.htm>>. For questions, please contact the RCR **Help Desk** by email at <[contact]>.

b. CTSU Registration Procedures

This study is supported by the NCI Cancer Trials Support Unit (CTSU).

1. **IRB Approval:**

Each investigator or group of investigators at a clinical site must obtain IRB approval for this protocol and submit IRB approval and supporting documentation to the CTSU Regulatory Office before they can be approved to enroll patients. Assignment of site registration status in the CTSU Regulatory Support System (RSS) uses extensive data to make a determination of whether a site has fulfilled all regulatory criteria including but not limited to: the following:

- An active Federal Wide Assurance (FWA) number
- An active roster affiliation with the Lead Network or a participating organization
- A valid IRB approval
- Compliance with all protocol specific requirements.

In addition, the site-protocol Principal Investigator (PI) must meet the following criteria:

- Active registration status
- The IRB number of the site IRB of record listed on their Form FDA 1572
- An active status on a participating roster at the registering site.

Sites participating on the NCI CIRB initiative that are approved by the CIRB for this study are not required to submit IRB approval documentation to the CTSU Regulatory Office. For sites using the CIRB, IRB approval information is received from the CIRB and applied to the RSS in an automated process. Signatory Institutions must submit a Study Specific Worksheet for Local Context (SSW) to the CIRB via IRB Manager to indicate their intent to open the study locally. The CIRB's approval of the SSW is then communicated to the CTSU Regulatory Office. In order for the SSW approval to be processed, the Signatory Institution must inform the CTSU which CIRB-approved institutions aligned with the Signatory Institution are participating in the study.

2. **Downloading Site Registration Documents:**

Site registration forms may be downloaded from the **S1316** protocol page located on the CTSU members' website.

- Go to <https://www.ctsu.org> and log in to the members' area using your CTEP-IAM username and password
- Click on the Protocols tab in the upper left of your screen
- Either enter the protocol # in the search field at the top of the protocol tree, or
- Click on the By Lead Organization folder to expand

- Click on the SWOG link to expand, then select trial protocol **S1316**
Click on LPO Documents, select the Site Registration documents link, and download and complete the forms provided.

CLOSED EFFECTIVE 5/15/2020

3. **Requirements For S1316 Site Registration:**

IRB approval (For sites not participating via the NCI CIRB; local IRB documentation, an IRB-signed CTSU IRB Certification Form, Protocol of Human Subjects Assurance Identification/IRB Certification/Declaration of Exemption Form, or combination is accepted)

